5.5. Exclusion Criteria – Stages 2 and 3 – Maternal Participants

Participants are excluded from the study if any of the following criteria apply:

- Investigator site staff members directly involved in the conduct of the study and their family members, site staff members otherwise supervised by the investigator, or participants who are Pfizer employees, including their family members, directly involved in the conduct of the study.
- Participants whose unborn baby have been fathered by investigational site staff members directly involved in the conduct of the study or their family members, site staff members otherwise supervised by the investigator, or Pfizer employees directly involved in the conduct of the study.
- For Stage 2 sentinel-cohort participants only, laboratory test results at the screening visit outside the normal reference range for pregnant women according to their trimester in pregnancy.
- Participation in other studies involving investigational drug(s), vaccines, or medical devices within 28 days prior to study entry and/or during study participation.
- History of severe adverse reaction associated with a vaccine and/or severe allergic reaction (eg, anaphylaxis) to any component of the investigational product or any related vaccine.

- 6. History of microbiologically proven invasive disease caused by GBS (S agalactiae), or
- 7. Current alcohol abuse or illicit drug use.

history of an infant with GBS disease.

Final Protocol Amendment 8, 27 March 2023

- Prepregnancy body mass index (BMI) of ≥40 kg/m². If prepregnancy BMI is not available, the BMI at the time of the first obstetric visit during the current pregnancy may be used.
- Clinical history of primary genital herpes simplex virus (HSV) infection during the current pregnancy.
- Participants with known or suspected immunodeficiency.
- 11. Participants who receive treatment with immunosuppressive therapy including cytotoxic agents or systemic corticosteroids, eg, for cancer or an autoimmune disease, or planned receipt through the postvaccination blood draw. If systemic corticosteroids have been administered short term (<14 days) for treatment of an acute illness, participants should not be enrolled into the study until corticosteroid therapy has been discontinued for at least 30 days before investigational product administration. Inhaled/nebulized, intra-articular, intrabursal, or topical (skin or eyes) corticosteroids are permitted.

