#### 2.2. Study Design

This is a Phase 1/2, randomized, placebo-controlled, observer-blinded trial to evaluate the safety, tolerability, and immunogenicity of a multivalent GBS6 vaccine in healthy 18- to 40-year-old nonpregnant women as well as pregnant women and their infants. Participants in Stage 2 will be vaccinated between 27 0/7 and 35 6/7 weeks' gestation, and participants in Stage 3 will be vaccinated between 24 0/7 and 35 6/7 weeks' gestation. A total of approximately 622 participants (66 nonpregnant women and 556 maternal participants and their infants) will be enrolled in this study.

## 2.2.1. Stage 1

Nonpregnant women in good health will be screened, enrolled, and randomized in a 1:1:1 ratio (approximately 22 participants enrolled/group) to receive placebo (saline control) or GBS6 (20 µg capsular polysaccharide [CPS]/serotype/dose) with or without aluminum phosphate (AlPO4) (see Table 2).

Stage 1 participants (nonpregnant women) willing and eligible to participate will return to receive a booster dose of GBS6 approximately 2 years after the primary dose of investigational product.

#### 2.2.2. Stage 2

Stage 2 will utilize a sentinel-cohort design, with cohort progression and dose escalation taking place after a safety review (data from each maternal participant through 14 days after vaccination) of the sentinel cohort of participants at each dose level. Pregnant women, once consented, will be referred to as "maternal participants". The first 42 eligible maternal participants at each dose level will compose a sentinel cohort. Starting with the lowest dose level, maternal participants will be randomly assigned (in a 1:1:1 ratio, 14 participants per group) to receive a single dose of GBS6, formulated with or without AlPO4, or placebo (saline control) within the sentinel cohort of a given dose level. Further enrollment will be expanded at each dose level until 78 additional participants are enrolled (expanded cohort).

Approximately 360 maternal participants are planned to be enrolled in Stage 2 (see Table 2).

#### 2.2.3. Stage 3

Approximately 196 additional maternal participants will be enrolled in Stage 3 to receive a single dose/formulation of the selected GBS6 or placebo (saline control) in a 1:1 ratio (see Table 2).

Table 2. Planned Participants: Total and Number in Each Stage and Group

Stage 1 D	ose/Formulation Group a (Nonpregnant Women)		Total (1:1:1)		

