#### Maternal Participants: Stage 2 Sentinel Cohort

Laboratory (hematology and chemistry) data will be collected for sentinel-cohort maternal participants only. Data are collected during the screening visit, Visit 0 (-14 to -2 days prior to vaccination), and will be considered baseline data. For participants with a rescreening visit, the rescreening laboratory results will be considered as the baseline data.

## Infant Participants: Stages 2 and 3

Day 1 is defined as the day of birth (Visit 1) for the infant participants, which corresponds to Visit 4 (delivery visit) for maternal participants.

Day 1 is considered the baseline visit for the following assessments: immunogenicity, physical examination, and vital signs.

If Day 1 is not available for noninfant participants, the most recent available data before vaccination will be considered as the baseline data.

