### 3.6.3. Laboratory Data

Laboratory data will be collected for the maternal participants (Stage 2 sentinel cohort) only at screening, at rescreening if applicable, and at Visit 2 (2-week follow-up visit). If abnormal laboratory parameters are reported at screening (Visit 0) or Visit 2 and the investigator believes the results to be erroneous, the abnormal laboratory parameters may be retested. In such cases, only the worst result will be used for summary. The parameters of interest at each visit are listed in Table 7.

Table 7. Laboratory Tests

Hematology	Chemistry
Hemoglobin	BUN and creatinine
Hematocrit	AST, ALT
RBC count	Total bilirubin
Platelet count	Alkaline phosphatase
WBC count	
Total neutrophils (Abs)	
Eosinophils (Abs)	
Monocytes (Abs)	
Basophils (Abs)	
Lymphocytes (Abs)	

Abbreviations: Abs = absolute; ALT = alanine aminotransferase; AST = aspartate aminotransferase; BUN = blood urea nitrogen; RBC = red blood cell; WBC = while blood cell.

The toxicity grading scale in Table 8 for maternal participants will be adapted, as appropriate at a specific time point (eg, based on the pregnancy status at the visit), for grading laboratory test abnormalities. For the grading scale, second trimester is defined as 14 1/7 through 28 0/7 weeks' gestation and third trimester as 28 1/7 weeks' gestation through delivery.

Table 8. Hematology and Blood Chemistry Toxicity Grading Scale for Maternal Participants

	Pregnancy Status	Normal Range	Mild (Grade 1)	Moderate (Grade 2)	Severe (Grade 3)	Grade 4
Female Hb, g/dL	Second trimester	9.7-14.8	9.0-9.6	8.0-8.9	7.0-7.9 or requires a transfusion	<7.0 or life-threatening acute blood loss
	Change from baseline		1.6-2.0	2.1-4.5	4.6-5.0	>5.0
	Third trimester	9.5–15.0	9.0-9.4	8.0-8.9	7.0-7.9 or requires a transfusion	<7.0 or life-threatening acute blood loss
	Change from baseline		1.6-2.0	2.1-4.5	4.6-5.0	>5.0

Table 8. Hematology and Blood Chemistry Toxicity Grading Scale for Maternal Participants

	Pregnancy	Normal	Mild	Moderate	Severe	
	Status	Range	(Grade 1)	(Grade 2)	(Grade 3)	Grade 4
Platelets high, 1000 cell/mm³	Second trimester	155-409	410-499	500-749	750-1000	>1000
	Third trimester	146-429	430-499	500-749	750-1000	>1000
Platelets low, 1000 cell/mm 	Second trimester	155-409	125-154	100-124	25-99	<25
	Third trimester	146-429	125-146	100-124	25-99	<25
WBC high, 1000 cell/mm 	Second trimester	5.6-14.8	>14.8-16.0	>16.0-20.0	>20.0-25.0	>25.0 signs of septic shock

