6.1.2. Primary Endpoint(s): Maternal Participants (Stages 2 and 3)

6.1.2.1. Proportion of Sentinel-Cohort Maternal Participants (Stage 2 Only) With Clinical Laboratory Abnormalities Following Administration of the Investigational Product at the 2-Week Follow-Up Visit

Endpoint: Abnormalities in safety laboratory parameters are based on the toxicity grading scale for pregnant women provided in Section 3.6.3.

- Analysis time point: Visit 2 (2 weeks after vaccination).
- Analysis population: Safety population for maternal participants (Stage 2 only).
- Analysis methodology: Descriptive summary statistics.
- Supporting objective: Primary safety objective.

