### Reporting results:

 Raw data: The n and proportion will be presented for laboratory parameters (eg, hemoglobin, WBC) normal and for each grade (1 through 4), by vaccine group, for sentinel-cohort maternal participants from Stage 2 only.

Figures: None.

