## 6.7.3. Laboratory Data

Descriptive summaries for laboratory abnormalities at 2 weeks after vaccination, as described in Section 3.6.3, will be provided by vaccine group. Also, separate listings for participants with abnormal laboratory results at 2 weeks after vaccination and participants retested for abnormal laboratory results at screening or 2 weeks after vaccination will be generated. These summaries and listings will be generated only for maternal participants (Stage 2 sentinel cohort).

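### Apart from banded hemoglobin change, the sentinel laboratory analysis makes no use of change from screening and names no continuous summary, so a moderate drift would seldom stand out from placebo

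*SAP*

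**What the plan says.** SAP 6.1.2.1 defines the endpoint by grade: "Abnormalities in safety laboratory parameters are based on the toxicity grading scale for pregnant women provided in Section 3.6.3". The stated output is the count and proportion "normal and for each grade (1 through 4), by vaccine group, for sentinel-cohort maternal participants from Stage 2 only". SAP 6.7.3 adds this: "Descriptive summaries for laboratory abnormalities at 2 weeks after vaccination, as described in Section 3.6.3, will be provided by vaccine group". It also plans listings of abnormal and retested results.

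The data for more are in hand. SAP 3.4 says of the screening panel: "Data are collected during the screening visit, Visit 0 (-14 to -2 days prior to vaccination), and will be considered baseline data". The same panel is drawn again at Visit 2. In SAP Table 8 the row "Change from baseline" appears for hemoglobin only, in both trimesters, with bands of 1.6-2.0, 2.1-4.5, 4.6-5.0 and >5.0 g/dL. Every other graded parameter is graded on its level at the visit. Table 7 lists 16 parameters; hematocrit and RBC count have no row in Table 8.

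On who is measured, SAP 3.4 states: "Laboratory (hematology and chemistry) data will be collected for sentinel-cohort maternal participants only". On numbers, SAP 2.2.2 states: "maternal participants will be randomly assigned (in a 1:1:1 ratio, 14 participants per group) to receive a single dose of GBS6". Protocol 5.5, criterion 3, excludes women on this ground: "For Stage 2 sentinel-cohort participants only, laboratory test results at the screening visit outside the normal reference range". SAP 5.2 and 5.2.1.3 define seven Stage 2 vaccine groups with a single placebo group.

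**The concern.** Protocol 2.2.5 describes the sentinel cohorts as the Phase 1 part of the study, focused on safety and including the safety laboratory tests. They are the only cohorts with scheduled post-vaccination hematology and chemistry. Every woman starts inside the normal range. For a parameter graded on level, a shift that stays inside the range therefore leaves no trace in the table, and one that reaches a limit shows as a few Grade 1 results. For hematocrit and RBC count, no shift of any size can appear in the graded table.

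SAP 5.1.1 adopts an estimation approach, so precision is the relevant standard. If the table is clean, a reader will want to know what size of drift it rules out. Grades in 14 women answer that poorly, although paired continuous values are already collected.

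**Working it through.** **The plan's own figure.** Protocol Table 9 gives the chance of at least one event among N as 1 − (1 − p)^N. For N = 14 and p = 10%, 1 − 0.9^14 = 0.77, as printed. The other five entries for N = 14 also reproduce.

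**Inputs.** From the documents: 14 women per GBS6 dose/formulation group; 28 per dose level with formulations combined; sentinel placebo 3 × 14 = 42. Assumed: values standardised to SD 1, normal range ±1.96 SD, baseline B restricted to that range, Visit 2 value Y = ρB + √(1 − ρ²)·E with E standard normal, ρ = 0.4 to 0.7, drift of 1 SD toward the limit.

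**Step 1, proportion beyond the limit.** P(Y > 1.96) with B in range is 2.3% (ρ = 0.4) to 1.8% (ρ = 0.7). With the drift, P(Y + 1 > 1.96) is 16.4% to 15.6%. That is about 2 women of 14.

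**Step 2, does anything appear?** With p near 0.16, 1 − 0.84^14 = 0.91. With p near 0.02 and no drift, 1 − 0.98^14 = 0.25. An isolated graded result is therefore likely under drift, and it is not rare without one.

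**Step 3, does a difference from placebo stand out?** The yardstick is two-sided 5%: exact Fisher power for the graded proportion, and noncentral t with noncentrality 1/[√(1 − ρ²)·√(1/n₁ + 1/n₂)] for the baseline-adjusted value. For 14 vs 42 and ρ = 0.4, √(1/14 + 1/42) = 0.309 and √(1 − 0.16) = 0.917, so the noncentrality is 1/(0.917 × 0.309) = 3.5 on 53 df.

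| 1-SD drift | Graded | Baseline-adjusted |
|---|---|---|
| 14 vs 42 | 0.34-0.35 | 0.93-0.99 |
| 28 vs 42 | 0.48-0.49 | 0.99 or more |

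Simulation with the restricted baseline gave the same adjusted values at 14 vs 42 (0.93 and 0.99).

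**Step 4, precision without a test.** The exact 95% CI is 0-23% for 0/14 graded and 2-43% for 2/14. The adjusted difference for 14 vs 42 has half-width t × √(1 − ρ²) × 0.309 with t = 2.006, that is 0.57 SD (ρ = 0.4) to 0.44 SD (ρ = 0.7). If the estimate is near zero, that interval excludes a 1-SD drift.

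**Step 5, hemoglobin.** In the third trimester the implied SD is (15.0 − 9.5)/3.92 = 1.40 g/dL. For ρ = 0.5 to 0.85, a 1-SD fall gives Grade 1 or higher, by level or by change, in about 48% of women, against 3-14% with no fall. Fisher power is 0.68-0.96 at 14 vs 42 and 0.87-0.996 at 28 vs 42. Hemoglobin is therefore reasonably served by its change rows.

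**The case against.** The protocol's endpoint is the proportion with clinical laboratory abnormalities, and grades answer that directly. They also match the stopping rules in Protocol 8.7, which act on Grade 3 and 4 laboratory results. A mean drift inside the pregnancy reference range is not an abnormality. This stands, and it is why the graded table should stay primary.

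The plan has no hypothesis tests, so power describes an analysis that nobody proposes. This is fair, and Step 4 makes the same point through interval width alone.

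Protocol 10.3.2 provides means, SDs and CIs for continuous safety outcomes where needed, SAP 5.2 promises descriptive statistics for all endpoints, and table shells are prepared separately. A continuous laboratory table may therefore be produced anyway. But none of this wording names laboratory values or change from screening, and the two sections on laboratory output name only abnormalities, grades and listings.

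A reader might infer three stronger things that the documents do not support:

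- That screening values are not used at all. Table 8 uses them for hemoglobin.
- That a 1-SD drift would usually leave no sign. At least one graded woman would usually appear; what is usually missing is a clear difference from placebo.
- That the comparison is 14 vs 14. With one Stage 2 placebo group, the sentinel comparator is 42.

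Nor are the sentinel cohorts the only possible source of laboratory data. Protocol 8.5 allows unscheduled tests, and Protocol 9.4.2 covers symptom-driven liver tests.

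**Conclusion.** The point holds as a modest improvement to the SAP; it does not show an error in the endpoint. Apart from hemoglobin, change from screening is unused. No parameter has a named continuous summary, and two of the 16 collected parameters cannot appear in the graded table.

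For a level-graded parameter drifting by 1 SD, the chance of a clear difference from pooled placebo is about 0.35 (14 vs 42) or 0.49 (28 vs 42) with grades, against 0.93 or more with baseline-adjusted values. These figures rest on normality, an SD inferred from the width of the normal range, and correlations of 0.4 to 0.7, none of which the documents supply. Skewed enzymes would give different numbers. Pooling placebo also assumes no systematic difference between the three successive sentinel cohorts.

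**What to change.** Keep the graded table as the primary endpoint and leave the stopping rules as they are. In SAP 6.1.2.1 and 6.7.3 add, for every Table 7 parameter:

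- mean (SD) and median at baseline and at Visit 2, and mean change with 95% CI, by vaccine group;
- a supportive baseline-adjusted (ANCOVA) difference from pooled sentinel placebo with 95% CI, on the log scale for ALT, AST, alkaline phosphatase and bilirubin, labelled descriptive and unadjusted for multiplicity.

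State one baseline rule for retested values. SAP 3.4 takes the rescreening result as baseline, while SAP 3.6.3 uses only the worst result for summary. For a woman admitted after a retest, the worst result could be the out-of-range value that the investigator thought erroneous.

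In the same edit, settle whether 6.1.2.1 reports CIs. It names none, while SAP 5.2.1.3 promises exact CIs for all primary safety endpoints.

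The cost is one table from data already collected, plus chance findings. Sixteen parameters × 9 contrasts (6 dose/formulation, 3 dose level) = 144 intervals, of which about 144 × 0.05 = 7 would exclude zero by chance. Limiting the adjusted contrasts to the 3 dose levels gives 16 × 3 = 48 intervals and 2 to 3 chance exclusions. SAP 6.7.1 already accepts unadjusted intervals for adverse events.

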# 6.1.2.2. Proportion of Maternal Participants Reporting Prompted Local Reactions Within 7 Days Following Administration of the Investigational Product

Endpoints: Maximum severity during the analysis time interval for pain at the injection site, redness, and swelling.

- Analysis time points: Days 1 through 7.
- Analysis population: Safety population for maternal participants (Stages 2 and 3).
- Analysis methodology: Descriptive summary statistics.
- Supporting objective: Primary safety objective.

#### Reporting results:

 Raw data: The numerator (n), denominator (N) used for the calculation of proportion, proportion, and associated 2-sided exact 95% CI will be presented for each severity (mild, moderate, severe, and Grade 4) of each local reaction, by vaccine group.

Figures: None.

# 6.1.2.3. Proportion of Maternal Participants Reporting Prompted Systemic Events Within 7 Days Following Administration of the Investigational Product

Endpoints: Maximum severity during the analysis time interval for fever, nausea/vomiting, diarrhea, headache, fatigue/tiredness, muscle pain, and joint pain.

- Analysis time points: Days 1 through 7.
- Analysis population: Safety population for maternal participants (Stages 2 and 3).
- Analysis methodology: Descriptive summary statistics.
- Supporting objective: Primary safety objective.

#### Reporting results:

 Raw data: The numerator (n), denominator (N) used for the calculation of proportion, proportion, and associated 2-sided exact 95% CI will be presented for each severity (mild, moderate, severe, and Grade 4) of each systemic event by vaccine group.

Figures: None.

# 6.1.2.4. Proportion of Maternal Participants Reporting AEs Through 1 Month After Administration of the Investigational Product

Endpoints: AEs experienced by maternal participants (Stages 2 and 3).

- Analysis time points: Day 1 to 1 month after vaccination.
- Analysis population: Safety population for maternal participants (Stages 2 and 3).
- Analysis methodology: Descriptive summary statistics.
- Supporting objective: Primary safety objective.

- Raw data: The number of participants with AEs (n), proportion, and associated 2-sided exact 95% CI will be presented for any AEs, SAEs, immediate AEs, severe AEs, related AEs, MAEs, and AEs leading to withdrawal, by vaccine group. Additionally, the number of participants with AEs (n), proportion, and associated 2-sided exact 95% CI will be presented for any AE, each SOC, and each preferred term within SOC, by vaccine group.
- Tier 2 AEs: The number of participants with AEs (n), proportion, risk difference, and associated 2-sided exact 95% CI will be presented for each preferred term.

Figures: None.

# 6.1.2.5. Proportion of Maternal Participants With SAEs, MAEs, and Obstetric Complications Through the 12-Month Postdelivery Visit

Endpoints: MAEs, SAEs, and obstetric complications by pregnancy period (prepartum, intrapartum, and postpartum) experienced by maternal participants (Stages 2 and 3).

- Analysis time points: Day 1 to the 12-month postdelivery visit.
- Analysis population: Safety population for maternal participants (Stages 2 and 3).
- Analysis methodology: Descriptive summary statistics.
- Supporting objective: Primary safety objective.

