- a. Visits at 2 weeks and 1 month after vaccination will not be performed if delivery occurs before the visits. In that case, hematology, and chemistry assessments due at the 2-week visit should be conducted at the delivery visit. Once delivery occurs, the visit windows are calculated based on delivery date.
- b. If abnormal laboratory values (as defined in Screening, Section 7.2.1, and in Section 8.5.3) are reported at Visit 0/Visit 2 and the investigator believes the results to be erroneous, the abnormal laboratory parameters may be retested.
- c. Vital signs include weight, height (only required at Visit 0), oral temperature, sitting blood pressure and pulse rate, and respiratory rate.
- d. Only concomitant medication taken to treat an adverse event will be recorded in the case report form.
- CCI
- f. Blood sample may be collected up to 72 hours after delivery.
- g. Participants will provide (in an e-diary) a baseline assessment of prompted systemic events prior to vaccination and participants will record (in an e-diary) reactogenicity events within a fixed time window each day for 7 days following vaccination. Remind participants that study staff may contact them to obtain additional information on Grade 3 events entered into the e-diary. Ask participants to contact the investigator or site staff immediately if they are prompted by the e-diary from Day 1 to Day 7 following vaccination to determine if an unscheduled visit is required (see Section 7.4).
- h. Designated site staff will review e diary data online at frequent intervals for the 7 days following vaccination to evaluate participant compliance and as part of the ongoing safety review.
- i. Only adverse events occurring up to 48 hours after each blood draw that are related to study procedures must be recorded in the case report form.

Stages 2 and 3 – Schedule o	f Activities	for Infant Par	ticipants				
Visit Number	1	2	3	4	5	6	7
Equivalent Visit Number for Maternal Participants	4	5	6	7	N/A	8	9
Visit Description	Delivery	1-Week Postdelivery Follow-Up	6-Week Postdelivery Follow-Up	14-Week Postdelivery Follow-Up	18-Week Postdelivery Follow-Up	6-Month Postdelivery Follow-Up	12-Month Postdelivery Follow-Up
Visit Window (Days)	Varies	7-10 Days After Visit 1	35-49 Days After Visit 1	80-100 Days After Visit 1	119-133 Days After Visit 1	160-200 Days After Visit 1	365-385 Days After Visit 1
Type of Visit	Hospital	Phone Call	Clinic	Clinic	Clinic	Phone Call	Clinic

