- Proportions of maternal participants reporting prompted local reactions within 7 days following administration of investigational product (pain at the injection site, redness, and swelling).
- Proportions of maternal participants reporting prompted systemic events within 7 days following administration of investigational product (fever, nausea/vomiting, diarrhea, headache, fatigue/tiredness, muscle pain, and joint pain).
- Proportions of maternal participants reporting AEs through 1 month after administration of investigational product.
- Proportions of maternal participants with SAEs, MAEs, and obstetric complications (prepartum, intrapartum, and postpartum) throughout the study (Visit 1 through the 12-month postdelivery study visit).
- Proportions of maternal participants with each delivery outcome (live birth, delivery mode).

3.1.6. Primary Safety Endpoints (Infant Participants): Stages 2 and 3

- Proportions of infant participants with specific birth outcomes.
- Proportions of infant participants with AEs from birth to 6 weeks of age.
- Proportions of infant participants with SAEs, AEs of special interest (major congenital anomalies, developmental delay, and suspected or confirmed GBS infection), and MAEs through 12 months of age.

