8.8.3. Medically Attended Adverse Events

MAEs will be assessed from screening for all participants up to Visit 4 (Stage 1) for nonpregnant participants, up to Visit 9 for maternal participants (Stages 2 and 3), and up to Visit 7 for infant participants (Stages 2 and 3). In addition, for participants receiving the booster vaccination in Stage 1, MAEs will be assessed from Visit 5 to Visit 10.

An MAE is defined as a nonserious AE that results in an evaluation at a medical facility.

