9.1.4.2. Stages 2 and 3 – Maternal Participants

In this study, the investigator and site staff will ensure the active elicitation and collection of AEs and SAEs through Visit 3. At 1 week following delivery (Visit 5), the participant will be contacted by telephone to inquire about MAEs and SAEs, including hospitalizations, since Visit 3. At all subsequent visits (Visits 6, 7, 8, and 9), only MAEs and SAEs, including hospitalizations, will be reported.

Immediate AEs will be reported as detailed in Section 8.8.2.

In addition, AEs occurring up to 48 hours after the Visit 4, Visit 6, and Visit 9 blood draws that are related to study procedures must be reported in the CRF.

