# 3.6.5. Obstetric Examination and Pregnancy Outcome: Maternal Participants (Stages 2 and 3)

Obstetric examination findings will be collected from screening (Visit 0) through the 1-month follow-up visit (Visit 3) and include the following: last menstrual period start date, certainty of menstrual start date (certain, uncertain, unknown), first and second trimester ultrasound dates, gestational age, method used to determine gestational age (last menstrual period, first trimester ultrasound, second trimester ultrasound, third trimester ultrasound, fundal height), estimated due date, vaginal examination status (normal, abnormal), fundal height (cm), fetal heart rate (beats/min), fetal movements (yes, no), investigator's assessment of fetal movement (normal, abnormal), fetal presentation (cephalic position, breech position, transverse position, unknown), and scars from previous deliveries (yes, no).

The following information regarding pregnancy outcome will be collected: date of delivery, location of delivery (medical facility, home, other), mode of delivery (vaginal, cesarean section), cesarean type (elective, semi-elective, emergency), delivery complications (yes, no), number of births, outcome at delivery (full-term live birth, premature live birth, stillbirth, spontaneous abortion, induced/elective abortion), gross visual inspection of the aborted fetus/stillbirth (not done, no observed abnormalities, observed abnormalities), and pathology performed (yes, no).

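### Obstetric complications are a primary maternal endpoint to 12 months, but after Visit 3 they are collected only as MAEs or SAEs, so the endpoint mixes two event definitions

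*SAP*

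**What the plan says.** **The endpoint.** Protocol Section 3.1.5 lists, among the primary maternal safety endpoints, "obstetric complications (prepartum, intrapartum, and postpartum) throughout the study (Visit 1 through the 12-month postdelivery study visit"). SAP Section 6.1.2.5 states the endpoint as "MAEs, SAEs, and obstetric complications by pregnancy period (prepartum, intrapartum, and postpartum) experienced by maternal participants (Stages 2 and 3"). The window it sets for this analysis is "Analysis time points: Day 1 to the 12-month postdelivery visit". The SAP tabulates obstetric complications for each pregnancy period by system organ class and preferred term, in addition to the SAE and MAE tables. Neither document defines the term for this endpoint or names its data source.

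**The collection rules.** Protocol Table 8 runs nonserious maternal AEs from consent to Visit 3, and SAEs and MAEs from consent to Visit 9. It has no row for obstetric complications, and SAP Section 3.6.1 adopts its periods. Under Protocol Section 9.1.4.2, the Visit 5 telephone contact asks about MAEs and SAEs since Visit 3, and then: "At all subsequent visits (Visits 6, 7, 8, and 9), only MAEs and SAEs, including hospitalizations, will be reported". For Visits 4, 6 and 9, note i of the maternal schedule says: "Only adverse events occurring up to 48 hours after each blood draw that are related to study procedures must be recorded in the case report".

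**What an MAE is.** Protocol Section 8.8.3: "An MAE is defined as a nonserious AE that results in an evaluation at a medical facility".

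**What the delivery form holds.** SAP Section 3.6.5 lists "delivery complications (yes, no") among the pregnancy outcome data. SAP Section 6.1.2.5 does not mention it.

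**The concern.** A component that the plan reports separately from SAEs and MAEs needs its own route into the data, or it adds nothing to them. Up to Visit 3 it has one, because any AE is recorded. After Visit 3 it has none: a complication reaches the coded AE data only if it is serious, medically attended or tied to a blood draw. One table row would then carry two event definitions, with a change of rule inside pregnancy that comes at different gestational ages in different women. A lower rate in a later period, or in women vaccinated early, could reflect the recording rule and not the women's experience. The plan handles a similar infant component differently: infant AEs of special interest have their own Table 8 row, from Visit 1 to Visit 7.

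**Working it through.** No stated figure is in dispute. The check sets the passages side by side, then places the changeover in gestational time.

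**1. Route into the data, by period**

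| Period | Collected | A nonserious complication is recorded if |
|---|---|---|
| Visit 1 to Visit 3 | all AEs | it is reported or observed |
| Visit 3 to delivery | MAEs, SAEs | it is classed as an MAE |
| Delivery, after Visit 3 | MAEs, SAEs, blood-draw AEs, delivery-complications item | it is classed as an MAE, or as yes/no on the form |
| Postpartum to Visit 9 | MAEs, SAEs, blood-draw AEs | it is classed as an MAE |

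The MAE definition turns on whether the event results in an evaluation at a medical facility. The documents do not say whether a complication arising in a woman already admitted for delivery meets that test, nor one found at a scheduled study visit.

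**2. Instructions that pull the other way**

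- Protocol Section 7.2.8 (Visit 6) sends abnormal findings of the targeted examination to the AE page as appropriate. SAP Section 3.6.4.2 says the same for Visit 6. Neither limits this to serious or medically attended events.
- Protocol Section 9.1.2 has the investigator record all directly observed and spontaneously reported AEs, with no time limit in that sentence.
- Section 9.1.4.2 and note i restrict recording at Visit 6.

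Two sites could each follow the protocol and treat the same nonserious Visit 6 finding differently.

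**3. Where the changeover falls**

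Inputs: Visit 3 is 28 to 42 days (4 to 6 weeks) after vaccination (Protocol Section 7.2.5). Vaccination is at 24 0/7 to 35 6/7 weeks in Stage 3 and from 27 0/7 in Stage 2 (Section 4). Delivery at 40 weeks is my reference point and is not stated in the plan.

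- Vaccinated at 24 0/7: Visit 3 at 24 + 4 = 28 0/7 to 24 + 6 = 30 0/7. To 40 weeks, 10 to 12 weeks remain under MAE/SAE-only recording.
- Vaccinated at 27 0/7: Visit 3 at 31 0/7 to 33 0/7, leaving 7 to 9 weeks.
- Vaccinated at 35 6/7: Visit 3 at 39 6/7 to 41 6/7, from 1 day before 40 weeks to 13 days after.

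So a term delivery falls after the changeover for early vaccination and can fall before it for late vaccination. Protocol Section 4.7.3 deliberately spreads Stage 3 vaccination across this range.

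**4. Precision**

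The plan's only precision figure for safety is Protocol Table 9. For N = 348 and a true rate of 1%, 1 − (1 − 0.01)^348 = 0.97, as printed. The formula treats every event as recorded. If a fraction c is captured, it becomes 1 − (1 − 0.01c)^N. The values of c below are assumed, because the documents give none:

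| c | N = 348 | N = 108 (Stage 3 GBS6 group) |
|---|---|---|
| 100% | 0.97 | 0.66 |
| 90% | 0.96 | 0.62 |
| 75% | 0.93 | 0.56 |
| 50% | 0.83 | 0.42 |

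This shows the direction of the effect and does not estimate it.

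**The case against.** The strongest reply is that the gap is narrow. Most of it stands.

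- **MAEs are nonserious by definition** and run to Visit 9, so a reader should not infer that nonserious complications after Visit 3 go uncounted in general. Only those not classed as MAEs are at risk.
- **Longer stays count.** Prolongation of an existing hospitalization is an SAE criterion (Protocol Section 9.2.3), and Section 9.2.4 includes transfer to an acute or intensive care unit. The carve-out for planned deliveries does not remove a complication that extends the admission.
- **Visit 6 findings may be recorded.** The instructions in step 2 could capture nonserious postpartum findings. They conflict with Section 9.1.4.2, so they leave the matter unsettled.
- **Late-vaccinated women** can deliver within the all-AE window. If delivery precedes Visit 3, the delivery visit replaces it, and Section 9.1.4 sets a minimum of 28 days of collection after vaccination.
- **No treatment difference is planned here.** SAP Section 6.1.2.5 gives proportions and intervals by group; risk differences are for Tier 2 AEs (SAP Section 5.2.1.3), and 6.1.2.5 has no Tier 2 item. Participants and assessors are blinded. A reader might infer a biased vaccine-placebo comparison, but the documents do not support that.
- **Study manuals are not available here.** The CRF and the study reference manual may give sites more guidance.

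What remains is the missing definition and source, the change of rule at Visit 3, and an unused delivery item.

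**Conclusion.** The mismatch is established from the text: a primary component from Visit 1 to 12 months has no collection category, and its event definition changes at Visit 3. What can be lost is limited to nonserious complications after Visit 3 that are not classed as MAEs. Intrapartum events have at least a yes/no record, but the SAP does not use it. Postpartum events have no equivalent item.

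The size cannot be derived. The loss in a reported proportion is p × f, where p is the true proportion and f the share unrecorded. Assuming p of 15% to 35% and f of 10% to 50%, the loss runs from 0.15 × 0.10 = 1.5 points to 0.35 × 0.50 = 17.5 points. Neither input has a source in the documents, and a range that wide should not be read as an estimate of bias. Loss should be similar across arms if blinding holds. It bears on absolute rates and on comparisons between pregnancy periods or gestational-age groups, and so also on setting Stage 2 beside Stage 3.

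**What to change.** In SAP Section 6.1.2.5:

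- **Intrapartum.** Count a woman if she has a coded AE, MAE or SAE of that type, or if the delivery-complications item on the pregnancy outcome form is yes. Keep the system organ class and preferred term table on coded events only, because a yes/no item cannot fill it.
- **Prepartum and postpartum.** Report prepartum complications split at Visit 3. Label the prepartum proportion after Visit 3 and the postpartum proportion as serious or medically attended complications, and restate the endpoint to match.

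Across both documents, reconcile Protocol Section 9.1.4.2 and note i with Protocol Sections 7.2.8 and 9.1.2 and SAP Section 3.6.4.2 on recording nonserious obstetric findings.

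Adding an obstetric-complication row to Table 8 looks the obvious remedy, but it comes too late. Protocol Section 4.1 says South Africa/UK enrollment is complete, so a new rule would apply to some women only and would itself mix ascertainment.

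Cost: one derivation, revised labels and no new collection. Both documents say that major changes to a primary endpoint definition go into a protocol amendment, so the restated endpoint probably needs one. The downsides are that the yes/no item adds uncoded events to the intrapartum proportion, and that the later-period endpoint is stated more narrowly.
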